The main objective is to evaluate the effectiveness of a multimodal intervention utilizing high-fidelity simulations of home health nursing care in enhancing the theoretical and practical skills of undergraduate nursing students for the care of patients with multimorbidity and heart failure.

This statistical analysis plan will provide a comprehensive overview of the study outcomes and their intended analysis.

2. Methods

2.1. Study design

A parallel randomized controlled trial (RCT) was conducted, employing a 1:1 allocation ratio for the control group (CG) and the experimental group (EG). The study adhered to the CONSORT 2025 (Consolidated Standards of Reporting Trials) (Hopewell et al., 2025a, 2025b) and INACSL (International Nursing Association of Clinical Simulation and Learning) recommendations for its proper execution. Recruitment commenced two weeks prior to the study's start, during which nursing students enrolled in the 'Family and Community Nursing I' course at the Faculty of Nursing were identified.

Subsequently, and prior to the study's commencement, an external researcher generated a randomization list for participants in blocks of sizes 4 and 6 using concealed random sequence generation software. Participants were then randomly assigned, with half allocated to the CG and the other half to the EG, respectively.

The intervention was conducted concurrently with the subject's scheduled teaching activities. The CG engaged in traditional learning, primarily theoretical instruction, and participated in simulations during the pretest and post-test phases without individual debriefing. In contrast, the EG received an individual debriefing report that included performance feedback and an audio-visual recording of their simulation. Following the pretest, the EG also attended a group debriefing session. Subsequently, they received specialized training on providing home visit care for patients with multimorbidity and heart failure, informed by clinical protocols and current scientific evidence.

The study was implemented from March (pretest) to April (post-test) 2025. No participants were lost during this period; however, the final data collection for satisfaction was extended until May 2025. The flow of the recruitment process and the study is depicted in Fig. 1.

[figure not shown]

Fig. 1. Flowchart of the design of the study conducted

2.2. Sample size calculation

As all students enrolled in the subject during the recruitment period constituted the study population, a sample size calculation was not applicable.

3. Outcomes

This section outlines the outcomes explored to address the main aim of the study. The details of these analyses can be found in Section 5.

3.1. Primary outcomes

3.1.1. Learning

Data collection for both the EG and the CG spanned from enrollment to the end of the 4-week intervention period, encompassing both pretest and post-test assessments.

Learning will be assessed through nursing students' performance during the simulations. Two independent observers, experienced in simulation-based teaching, evaluated each simulation (pretest and post-test) using a validated checklist specific to each scenario. The checklist measures the following aspects: (1) assessment of patients and home environment observation (4 items), (2) nursing intervention (5 items), and (3) transferable skills related to greeting, farewell, and communication (5 items). Each item is scored dichotomously (Yes/No), and a final overall evaluation (0-10 points) is provided. The inter-observer agreement will be determined by Cohen's kappa.

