5.1. Primary outcomes

Univariate statistics will be performed for the learning and empathy outcomes. Continuous variables will be reported using summary measures (means or medians) and measures of dispersion (standard deviation or interquartile range). Categorical variables will be presented as frequencies and percentages.

For bivariate analyses, the chi-square test or Fisher's exact test will be employed for qualitative variables. The Shapiro-Wilk test will be used to assess the normality of quantitative variables. Intergroup analysis will then be conducted using Student's t-test for independent samples if distributions are normal, and the Mann-Whitney U-test for non-normal distributions. For intra-group analysis (pre-test vs. post-test), Student's t-test for paired samples will be applied for normal distributions, with the Wilcoxon signed-rank test used when this premise is not met. For relationships between quantitative variables, Pearson's correlation will be utilized for normal distributions, while Spearman's rank correlation will be used for non-normal distributions.

The level of significance or type I error to be used is 0.05. Likewise, the effect size will be determined in case of significant differences using Cohen's d, Rosenthal's r, Cramer's V, among others.

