2.2. Pre-post test

* Encoding: UTF-8.

SORT CASES BY Group.

SPLIT FILE SEPARATE BY Group.

FREQUENCIES VARIABLES=PRE_AO PRE_NI PRE_TC PRE_Total POST_AO POST_NI POST_TC POST_Total

/NTILES=4

/STATISTICS=STDDEV VARIANCE RANGE MINIMUM MAXIMUM MEAN MEDIAN MODE SUM SKEWNESS SESKEW KURTOSIS

SEKURT

/ORDER=ANALYSIS.

FREQUENCIES VARIABLES=PRE_AO PRE_NI PRE_TC PRE_Total POST_AO POST_NI POST_TC POST_Total

/NTILES=4

/STATISTICS=STDDEV VARIANCE RANGE MINIMUM MAXIMUM MEAN MEDIAN MODE SUM SKEWNESS SESKEW KURTOSIS

SEKURT

/ORDER=ANALYSIS.

NPAR TESTS

/WILCOXON=PRE_AO PRE_NI PRE_TC PRE_Total WITH POST_AO POST_NI POST_TC POST_Total (PAIRED)

/MISSING ANALYSIS.

SPLIT FILE OFF.

NPAR TESTS

/M-W= PRE_AO PRE_NI PRE_TC PRE_Total POST_AO POST_NI POST_TC POST_Total BY Group(1 2)

/MISSING ANALYSIS.

3. Empathy

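### Within-arm pre-post tests of learning cannot separate learning from a change in scenario difficulty, and the SAP does not rank them below the between-arm comparison

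*SAP*

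**What the plan says.** Section 3.1.1 makes learning a primary outcome. Two observers rate every simulation, at pretest and at post-test, "using a validated checklist specific to each scenario". The checklist has three domains of 4, 5 and 5 items, and "Each item is scored dichotomously (Yes/No), and a final overall evaluation (0-10 points) is provided".

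Section 5.1 sets out two kinds of comparison for the primary outcomes. One is between groups. The other is within each group: "For intra-group analysis (pre-test vs. post-test), Student's t-test for paired samples will be applied for normal distributions", with the Wilcoxon signed-rank test as the non-normal alternative. One error level serves both: "The level of significance or type I error to be used is 0.05". The section does not say which kind of comparison decides whether the intervention worked.

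The Analytic Code, section 2.2 (Learning, Pre-post test), carries out both. With the file split by group it runs "WILCOXON=PRE_AO PRE_NI PRE_TC PRE_Total WITH POST_AO POST_NI POST_TC POST_Total (PAIRED"; with the split off it runs "M-W= PRE_AO PRE_NI PRE_TC PRE_Total POST_AO POST_NI POST_TC POST_Total BY Group(1 2". The second command compares the arms at pretest and at post-test separately. There is no between-arm test of change and no baseline-adjusted model.

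**The concern.** A paired test asks whether post-test minus pretest is centred on zero. That answers a question about learning only if the two scores are on one scale. If each phase used its own scenario and its own checklist, the difference holds two things: the change in skill and the change in difficulty. An easier post-test scenario would look like improvement in an arm that learned nothing, and a harder one would hide real learning. Data from a single arm cannot separate the two.

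This problem does not arise in the same form for empathy, where section 3.1.2 uses one fixed 20-item scale at both times. At stake is how the learning result is read. Because the plan does not rank its tests, a report could present a significant change in the experimental group, or its absence in the control group, as the evidence of effectiveness.

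**Working it through.** **How much of the plan is exposed.** Counted from the Analytic Code:

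- Learning, paired: 4 scores (AO, NI, TC, Total) × 2 arms = 8.
- Learning, between arms: 4 scores × 2 phases = 8.
- Empathy: 1 score × 2 arms = 2 paired, and 2 between arms.

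The paired learning tests are therefore 8 of 16 learning tests (50%) and 8 of 8 + 8 + 2 + 2 = 20 coded tests on the primary outcomes (40%). Four of the between-arm learning tests concern the pretest only. Of the 8 + 4 = 12 learning tests that use post-test data, 8 are within-arm.

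**Why one comparison is exposed and the other is not.** Let L_E and L_C be the mean gains in the two arms and δ the shift in difficulty between the phases.

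- Within an arm, the expected change is L + δ. The paired test rejects when L + δ is far from zero, whatever L is.
- Between arms, (L_E + δ) − (L_C + δ) = L_E − L_C. The shift cancels if both arms meet the same scenarios.
- In a model post = a + b·pre + τ·group, δ goes into a and any difference in scale goes into b. τ needs no common scale.

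**Size.** The SAP gives no number of students and no variance, so there is no figure of its own to reproduce. Assumptions: 30 to 50 students per arm, pre-post correlation r of 0.3 to 0.7, normal scores with equal SD, no learning, two-sided 0.05 (the SAP does not state sidedness). With δ in SD units:

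standardised change = δ / √(2(1 − r)); noncentrality = √n × standardised change.

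- n = 30, r = 0.3, δ = 0.2: 0.2/√1.4 = 0.169; × √30 = 0.93; a paired t-test rejects in 15%. Simulated Wilcoxon runs give about 13% to 16%.
- n = 30, r = 0.5, δ = 0.3: 0.3/√1 = 0.3; × √30 = 1.64; t-test 36%, Wilcoxon about 35%.
- n = 50, r = 0.5, δ = 0.3: 0.3 × √50 = 2.12; t-test 55%, Wilcoxon 53%.
- n = 50, r = 0.7, δ = 0.5: 0.5/√0.6 = 0.645; × √50 = 4.56; both 99%.

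Simulated Wilcoxon rejection rates with no learning (3,000 replicates; first figure n = 30, second n = 50):

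| δ (SD) | r = 0.3 | r = 0.5 | r = 0.7 |
|---|---|---|---|
| 0.2 | 16–21% | 18–27% | 27–42% |
| 0.3 | 27–41% | 35–53% | 52–74% |
| 0.5 | 59–81% | 73–93% | 91–99% |

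With δ = 0 the rate is about 5% throughout.

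**Check with discrete scores.** Normal scores ignore ties, so the same question was simulated with 14 Yes/No items per phase (1,500 replicates, assumed pretest pass rate 0.60, ability SD 0.6 on the logit scale, no learning):

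| Post-test pass rate | Shift in items | n = 20 | n = 30 | n = 50 |
|---|---|---|---|---|
| 0.60 | 0 | 5% | 5% | 4–6% |
| 0.65 | 14 × 0.05 = 0.7 | 17–20% | 28% | 43–46% |
| 0.70 | 14 × 0.10 = 1.4 | 61–62% | 80–81% | 96% |

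In every one of these settings the between-arm Mann-Whitney test on the post-test total rejected in 4% to 6%.

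**The case against.** The strongest reply is that the SAP never says the pretest and post-test scenarios differ. It does not give the number of scenarios or how they were assigned to phases. If the same scenarios were repeated or rotated across phases, the wording could be the same and the bias would shrink or vanish. Section 3.1.1 goes on to describe the checklist in the singular, with one 4/5/5 structure. Analytic Code 2.1 tabulates one set of 14 item names split by group and phase. The communication domain (greeting, farewell) may depend little on the scenario. All of this stands: a reader might infer that different item sets are a fact, and the document does not support that. It does not settle the matter the other way either, since equal item counts and shared variable names do not show equal difficulty.

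A second reply is that equating and counterbalancing may be described in the protocol. That is fair, and their absence here is not itself the fault. What the SAP does fix is an unranked set of tests, some of which depend on comparability.

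Third, the valid comparison is already planned. Both arms take part in simulations at both phases (section 2.1), the between-arm post-test test is coded, and a pure difficulty shift would tend to show in the control arm too. This stands and limits the damage. A reader might conclude that the trial's group contrast is biased, or that half of the primary analysis fails; neither follows. The first is protected if both arms meet the same scenarios, and the share across both primary outcomes is 8 of 20.

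Finally, the error rates rest on assumed n, correlation and shift. They show how sensitive the test is, not what happened in this trial.

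**Conclusion.** The point holds in a limited form. As planned, the within-arm paired learning tests cannot distinguish learning from a change in scenario difficulty, or from any other effect of time. The SAP places them under the primary outcomes without ranking them below the randomised comparison. That different item sets were used before and after is the natural reading of section 3.1.1, but it is an inference. The direction and size of any bias are unknown: over the assumed ranges, the chance of a significant result with no learning runs from about 13% to 99%. The between-arm post-test comparison keeps its nominal 5% if both arms meet the same scenarios. The trial can still answer its question, provided the learning conclusion is drawn from that comparison.

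**What to change.** Report pretest and post-test AO, NI, TC and Total scores by arm descriptively, without within-arm p-values as evidence of effectiveness. State that the learning conclusion rests on the between-arm comparison of post-test scores with the pretest score as covariate, for example ANCOVA or a rank-based equivalent. State also whether the pretest and post-test scenarios were the same, equated or counterbalanced, and whether both arms met the same ones.

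The cost is one added model (neither section 5.1 nor the code contains an adjusted analysis), one sentence on which comparison decides, and the loss of within-arm p-values as evidence of effectiveness. No new data are needed, because the pretest score is already collected. The Analytic Code records the analysis as completed on 2025-06-30, so the change would be made in reporting, with the adjusted model labelled as added after that date.

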3.1.2. Empathy

Data collection for both the EG and the CG was conducted from enrollment through the conclusion of the 4-week intervention, encompassing both pretest and post-test assessments.

Empathy toward patients presenting with multimorbidity and heart failure is essential for providing professional care. Students' empathy levels were assessed using the Spanish version of the *Jefferson Scale of Empathy, student version* (JSE-S), which demonstrated a Cronbach's alpha coefficient of 0.90 (Díez et al., 2022). The JSE-S is a 20-item instrument specifically developed to measure empathy in health professions education and patient care, suitable for administration to both students and practitioners. Items are rated on a 7-point Likert-type scale (1 = Strongly Disagree, 7 = Strongly Agree). Half of the items are positively worded and directly scored, while the other half are negatively worded and reverse-scored. The total score ranges from 20 to 140, with higher scores indicating greater empathy.

3.2. Secondary outcomes

3.2.1. Self-confidence in learning

Data collection for the EG and the CG occurred from student enrollment through the conclusion of the 5-week intervention period, encompassing both pretest and post-test assessments.

Student satisfaction and self-confidence in learning were measured immediately after each simulation using the *Student Satisfaction and Self-Confidence in Learning Scale* (SCLS). This scale utilizes a five-point Likert-type format, with responses ranging from 'strongly disagree' to 'strongly agree'. Possible scores on the SCLS range from 13 to 65 points. Its Spanish version was validated with a Cronbach's alpha coefficient of 0.90 (Farres-Tarafa et al., 2021).

3.2.2. Quality of simulations

Data collection for the EG and the CG spanned from student enrollment to the conclusion of the 5-week intervention period. For the EG, both pre-test and post-test assessments were conducted, while the CG underwent only post-test evaluation.

Following the individual and group debriefings, the *Educational Practices Questionnaire (student version)* (EPQ) was administered. This questionnaire comprises 16 items, each rated on two separate 5-point scales to assess both quality and importance. The Spanish version of the EPQ was validated with Cronbach's alpha coefficients of 0.86 and 0.91 for its respective scales (Román-Cereto et al., 2022).

3.2.3. Satisfaction on simulations

Data collection for the EG and the CG spanned from student enrollment to the conclusion of the 5-week intervention period. For the EG, both pre-test and post-test assessments were conducted, while the CG underwent only post-test evaluation.

Following the individual and group debriefings, student satisfaction with the high-fidelity clinical simulation was assessed using the *High Fidelity Clinical Simulation Satisfaction Scale in Students* (ESSAF). This scale comprises 33 statements, each rated on a 5-point Likert-type scale ranging from 1 (strongly disagree) to 5 (strongly agree). The 33 items are categorized into eight factors or dimensions reflecting student perception of the simulation experience: 'Usefulness,' 'Characteristics of cases and applications,' 'Communication,' 'Perceived performance,' 'Increased self-confidence,' 'Relationship between theory and practice,' 'Facilities and equipment,' and 'Positive aspects.' The ESSAF was validated with a Cronbach's alpha coefficient of 0.857 (Alconero-Camarero et al., 2019).

4. Study population

The study population comprised the entire cohort of students, who were randomly allocated in a 1:1 ratio to either the EG or the CG. A two-month follow-up period was established, and no participant attrition occurred during the intervention.

Baseline data included socio-demographic, academic, and occupational information, specifically: gender, age, number of cohabitants, housing type, academic level, and occupation during their studies. Additionally, personal experiences related to family care were gathered using dichotomous response items. Given the nature of the participants and the relatively modest population size, no intervention subgroups were formed.

5. Data analysis

An external researcher, expert in univariate and bivariate statistics, including effect size determination, will perform the database recording and statistical analysis. This investigator will be blinded to participant group allocation and will have full access to all collected data.

To meet the study objectives, the researcher will use the latest version of the statistical analysis plan (SAP), as published in the protocol registered on *ClinicalTrials.gov* (NCT06855719), to derive the necessary statistical results for the outcomes. SPSS statistical software will be utilized for this purpose. The analysis is scheduled to be conducted between May and June 2025.

5.1. Primary outcomes

Univariate statistics will be performed for the learning and empathy outcomes. Continuous variables will be reported using summary measures (means or medians) and measures of dispersion (standard deviation or interquartile range). Categorical variables will be presented as frequencies and percentages.

For bivariate analyses, the chi-square test or Fisher's exact test will be employed for qualitative variables. The Shapiro-Wilk test will be used to assess the normality of quantitative variables. Intergroup analysis will then be conducted using Student's t-test for independent samples if distributions are normal, and the Mann-Whitney U-test for non-normal distributions. For intra-group analysis (pre-test vs. post-test), Student's t-test for paired samples will be applied for normal distributions, with the Wilcoxon signed-rank test used when this premise is not met. For relationships between quantitative variables, Pearson's correlation will be utilized for normal distributions, while Spearman's rank correlation will be used for non-normal distributions.

The level of significance or type I error to be used is 0.05. Likewise, the effect size will be determined in case of significant differences using Cohen's d, Rosenthal's r, Cramer's V, among others.

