3.2. Pre-post test

```
* Encoding: UTF-8.  
SORT CASES BY Group.  
SPLIT FILE SEPARATE BY Group.  
EXAMINE VARIABLES=Pretest Posttest  
/PLOT NPLOT  
/STATISTICS NONE  
/CINTERVAL 95  
/MISSING LISTWISE  
/NOTOTAL.  
NPAR TESTS  
/WILCOXON=Pretest WITH Posttest (PAIRED)  
/MISSING ANALYSIS.  
SPLIT FILE OFF.  
NPAR TESTS  
/M-W= Pretest Posttest BY Group(1 2)  
/MISSING ANALYSIS.
```

4. Self-confidence in learning

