4.2. Pre-post test

```
* Encoding: UTF-8.  
SORT CASES BY Group.  
SPLIT FILE SEPARATE BY Group.  
EXAMINE VARIABLES=PRE_Satisfaction_D1 PRE_Self_Confidence_D2 TOTAL_Pretest POST_Satisfaction_D1  
    POST_Self_Confidence_D2 TOTAL_Posttest  
/PLOT NPLOT  
/STATISTICS NONE  
/CINTERVAL 95  
/MISSING LISTWISE  
/NOTOTAL.  
NPAR TESTS  
/WILCOXON=PRE_Satisfaction_D1 PRE_Self_Confidence_D2 TOTAL_Pretest WITH POST_Satisfaction_D1  
    POST_Self_Confidence_D2 TOTAL_Posttest (PAIRED)  
/MISSING ANALYSIS.  
SPLIT FILE OFF.  
NPAR TESTS  
/M-W= PRE_Satisfaction_D1 PRE_Self_Confidence_D2 TOTAL_Pretest POST_Satisfaction_D1  
    POST_Self_Confidence_D2 TOTAL_Posttest BY Group(1 2)  
/MISSING ANALYSIS.
```

5. Quality of simulations

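### Learning, empathy and SCLS are compared between arms without using the pretest, and no test is named as deciding effectiveness

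*SAP*

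**What the plan says.** Between arms, SAP section 5.1 (Primary outcomes) states: "Intergroup analysis will then be conducted using Student's t-test for independent samples if distributions are normal, and the Mann-Whitney U-test for non-normal distributions". Within arms it states: "For intra-group analysis (pre-test vs. post-test), Student's t-test for paired samples will be applied for normal distributions", with the Wilcoxon signed-rank test otherwise. Section 5.2 carries the same methods over to the secondary outcomes, which include SCLS.

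The Analytic Code follows this pattern. For each outcome it runs Wilcoxon tests separately by group and then Mann-Whitney tests on the pretest and post-test scores, each taken alone:

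- Learning, code section 2.2: "M-W= PRE_AO PRE_NI PRE_TC PRE_Total POST_AO POST_NI POST_TC POST_Total BY Group(1 2"
- Empathy, code section 3.2: "M-W= Pretest Posttest BY Group(1 2"
- SCLS, code section 4.2: "M-W= PRE_Satisfaction_D1 PRE_Self_Confidence_D2 TOTAL_Pretest POST_Satisfaction_D1", continuing with the remaining post-test scores

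Sections 3.1.1, 3.1.2 and 3.2.1 give both arms a pretest and a post-test on these three outcomes, and section 6 reports no missing data. The SCLS pretest qualifies as a baseline: "Student satisfaction and self-confidence in learning were measured immediately after each simulation", and section 2.1 places the group debriefing after the pretest. EPQ and ESSAF have no control-group pretest (sections 3.2.2 and 3.2.3), so this point does not concern them.

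**The concern.** The stated objective is the effectiveness of the intervention, which is a question about the difference between arms. Two things are fixed badly.

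First, the plan does not say which test answers that question. Between-arm and within-arm tests stand side by side at the 0.05 level. A within-arm p-value does not estimate the intervention effect. Both arms take part in the pretest and post-test simulations, so both may improve for reasons unrelated to the intervention. If the experimental arm shows a significant gain, the control arm does not, and the arm difference is not significant, the plan gives no rule for which result counts.

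Second, the arm comparison ignores a pretest already collected on every student. The whole enrolled cohort was taken (section 2.2), so precision could not be bought with more students. Adjusting for the pretest was the available way to gain it.

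**Working it through.** **Inputs from the SAP.** 1:1 individual randomisation (section 2.1); significance level 0.05, sidedness not stated and taken as two-sided (section 5.1); pretest and post-test in both arms (sections 3.1.1, 3.1.2, 3.2.1). Section 2.2 gives no sample size calculation, and no number per arm, SD, effect size or pre-post correlation is stated. The plan therefore has no figure to reproduce.

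**Assumptions.** Pre-post correlation (rho) 0.3 to 0.7; 25 to 60 per arm; standardised difference d = 0.5; normally distributed scores.

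**1. What the code tests.** Each score gets four tests: Wilcoxon in each arm, Mann-Whitney on the pretest, and Mann-Whitney on the post-test. That gives 4 × 4 = 16 tests for learning, 1 × 4 = 4 for empathy and 3 × 4 = 12 for SCLS. Only the post-test Mann-Whitney addresses the intervention effect, and it does not use the pretest. There is no ANCOVA, change-score comparison or group-by-time term.

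**2. Validity.** With no true arm difference, the post-test Mann-Whitney rejected in 4.2% to 5.3% of simulated trials (25, 40 and 60 per arm; rho 0.3, 0.5, 0.7; 3,000 trials per setting). The unadjusted comparison is valid.

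**3. Precision.** Variance of the adjusted difference relative to the unadjusted one is 1 − rho². The interval narrows by 1 − √(1 − rho²), and the equivalent sample-size multiplier is 1/(1 − rho²).

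| rho | variance ratio | interval narrower by | sample-size multiplier |
|---|---|---|---|
| 0.3 | 0.91 | 4.6% | 1.10 |
| 0.5 | 0.75 | 13.4% | 1.33 |
| 0.7 | 0.51 | 28.6% | 1.96 |

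Learning may lie at the low end, because it is scored "using a validated checklist specific to each scenario" and the pretest and post-test scores may correlate less.

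**4. Power at d = 0.5** (4,000 simulated trials per setting; ANCOVA values at rho 0.3 / 0.5 / 0.7):

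| per arm | Mann-Whitney | rank ANCOVA | linear ANCOVA |
|---|---|---|---|
| 25 | 0.37–0.39 | 0.40 / 0.47 / 0.62 | – |
| 35 | 0.50–0.52 | 0.53 / 0.62 / 0.77 | 0.56 / 0.66 / 0.81 |
| 50 | 0.67–0.68 | 0.71 / 0.79 / 0.91 | – |

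**5. Conflict between the tests.** Suppose both arms truly gain the same amount and each within-arm test has power p. Only the experimental arm is then significant with probability p(1 − p): 0.3 × 0.7 = 0.21, 0.5 × 0.5 = 0.25, 0.8 × 0.2 = 0.16.

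Simulated with 35 per arm, rho 0.5 and 6,000 trials per setting:

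| equal gain (SD) | within-arm power | experimental arm only significant | of all trials: that, and post-test Mann-Whitney not significant |
|---|---|---|---|
| 0.25 | 28% | 0.199 | 0.186 |
| 0.34 | 48% | 0.249 | 0.233 |
| 0.50 | 80% | 0.160 | 0.149 |

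The last column over the one before it is about 93% in each row. A separate simulation with paired t-tests, an equal gain of 0.3 SD, 25 to 60 per arm and rho 0.3 to 0.7 gave experimental-arm-only significance in 12% to 25% of trials.

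**The case against.** A simple unadjusted test that is valid is an acceptable choice, and preferring a more efficient one is not the same as finding an error. This stands in part: the precision loss is a missed improvement, and the unnamed deciding test is the weightier half.

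The size of the gain is uncertain. Number per arm, correlation and effect size are all assumed. The interval that would narrow is one the SAP does not plan, since section 5.1 reports effect sizes only after significant results. Setting linear ANCOVA against Mann-Whitney also mixes two effects, because on normal scores at 35 per arm a plain t-test already has power of about 0.54. These points stand. The like-for-like comparison is rank ANCOVA against Mann-Whitney, and at rho 0.3 its gain is only 2 to 3 points. Bounded scores reduce it too: in an illustrative case clipped to 0–5 near its ceiling with latent rho 0.7, power rose from 0.45 to 0.63, 18 points against about 25 on normal scores.

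The p(1 − p) figures describe a reading that the SAP never prescribes, and 25% is their mathematical maximum. They are indeed not an error rate of the plan. They show how often the planned tests would invite that reading, and the plan does not rule it out.

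Naming a deciding test now is as post hoc as adding an ANCOVA. That is right, and the fix must say so. Finally, dropping the pretest significance tests removes a formal check on the baseline. The code's descriptive output by group and phase (sections 2.1, 3.1 and 4.1) still shows any imbalance.

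**Conclusion.** The concern holds. For learning, empathy and SCLS, text and code contain no arm comparison that uses the pretest, and no sentence says which test decides effectiveness. The planned post-test comparison is valid, so no bias is claimed.

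The more serious part is the missing rule. With equal true gains, the planned tests point different ways in about 19%, 23% or 15% of trials, assuming 35 per arm, rho 0.5 and within-arm power of 28%, 48% or 80%. The precision loss equals forgoing about 10%, 33% or 96% more students at rho 0.3, 0.5 or 0.7. It is small at the low end, where learning may lie. The facts are certain; the sizes depend on a number per arm and a correlation that the SAP does not give. The point should be corrected, but it does not invalidate the trial.

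**What to change.** 1. State that effectiveness is judged on the between-arm post-test comparison of the total score for learning, JSE-S and SCLS. Present within-arm changes as descriptive and drop the significance tests of pretest scores by group.
2. Add an ANCOVA of the post-test total on group with the pretest total as covariate, and report the adjusted difference with a 95% confidence interval. For learning: `UNIANOVA POST_Total BY Group WITH PRE_Total /PRINT=PARAMETER`, and likewise for the other two. If residuals are clearly non-normal, use a rank-based version or a bootstrap interval.
3. The analysis is recorded as complete on 2025-06-30, so label the ANCOVA post hoc and show it beside the planned comparison, not in its place. Date the statement in step 1 as added after the analysis too.
4. State whether the pretests were taken and scored without knowledge of allocation, which the adjustment assumes. The question arises because, before the study began, "an external researcher generated a randomization list for participants in blocks of sizes 4 and 6".

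The cost is a paragraph of SAP wording and a few lines of SPSS code, with no new data. The price of acting now is that neither addition can be presented as prespecified.
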